## Overview

The *Healthy Detours* app will be tested in a 12-week randomized controlled trial (RCT) with 300 college students at Louisiana State University (LSU) during the Fall 2016 and Spring 2017 semesters. RCT enrollment will be split between these two semesters, with approximately 150 students enrolling during each 12-week period. Students will be randomized to either the *Healthy Detours* app or to an active control condition app.

USDA's *SuperTracker* was originally proposed to serve as the control app for the research project. However, only the *SuperTracker* web page is currently functioning, thereby eliminating it as an appropriate control condition for the *Healthy Detours* app.

The research team agreed on the following criteria for the control app:

- Must be publically available at no cost to the user
- Must be compatible with both Android and iPhone platforms
- Must come from a reputable source
- Must not be an app specifically designed for weight loss; weight monitoring apps may be included

Based on these criteria, *Calorie Counter* by FatSecret was selected as the RCT control condition app.

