### **Step 1: Study Orientation**

PBRC staff will provide an overview of the study with a PowerPoint presentation. They will explain the purpose of the study, participant inclusion, study procedures, and participant compensation. Participants will be informed that they are expected to frequently use the app, and that their back end data will be tracked. Staff will notify participants that they will receive the 6-week interim survey link via email, and that they may receive app updates throughout the 12-week period. Participants will be instructed to download any app updates they may receive.

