## Step 4: Randomization

Participants should be instructed to notify PBRC staff once they have finished the ASA24. At this point, participants will be randomized to their study condition. The randomization link for each participant will be within the individual's Healthy Detours Schedule Page. PBRC staff will click on this link to determine the participant's study condition.

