The analyses are heavily descriptive in nature for this feasibility trial. Means (standard deviations), medians (Interquartile range), distributions, frequencies and percentiles, etc. will be used to characterize the major outcome measures. Tests will be performed as per the design using simple t-tests followed by analysis of covariance to assess the outcome results adjusted for baseline (rather than change from baseline). Multivariate analyses will be conducted to assess the simultaneous direction of changes between the treatment arms. We will test the four outcomes simultaneously and examine the correlation amongst them within treatment arms. Hotelling’s T2 will be used to test the overall mean vector of responses. This analysis will utilize the pre and post measures, but additional analyses will be conducted using generalized least squares regression (PROC MIXED in SAS ver 9.3 or higher) to account for missing data (drop outs between 6 weeks and 12 weeks).

Characteristics of dropouts will be intensively examined to shed light on potential weaknesses of the app (differential dropout overall or within certain subgroups). The evaluation of the control app will include its impact using the pre-post data. This will provide information on the choice of this app as the relevant control population. As noted, examination of the correlation matrices along with the mean changes will inform whether the variables appear to move similarly in both groups. Thus, one might argue that it not necessarily the best control choice since we would then be measuring the intensity of intervention. Alternatively, very different correlation structures will inform us about how the interventions are working and may provide information on appropriate controls and or strengths and weaknesses.

Utilization data will be examined to understand the acceptability and intensity of interactions with the apps. The penetration of the apps into this young at-risk population is very important in potentially understanding, not only market share, but also potential impact. Complier average causal effect models²¹⁷ will be used to examine the intensity of the intervention app's utilization. Mediation models using the latest bootstrapping methods^{218,219} will be examined to enhance evidence that the changes induced by the treatment effects are consistent with the changes being mediated via the app and the Healthy Detours intervention.

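### Enrollment runs as two semester cohorts, but no planned model names semester; pre-specifying it as a fixed effect is a minor, nearly free gain in precision

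*Protocol*

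**What the plan says.** The Protocol's Overview plans 300 students in two cohorts: "RCT enrollment will be split between these two semesters", with "approximately 150 students enrolling during each 12-week period". On allocation it says "Students will be randomized to either the *Healthy Detours* app or to an active control condition app", and under Step 4: Randomization that "PBRC staff will click on this link to determine the participant's study condition". No ratio, blocking or stratification factor is stated anywhere.

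The SAP's paragraph on tests starts with t-tests and goes on to "analysis of covariance to assess the outcome results adjusted for baseline". It then adds Hotelling's T2 on the four outcomes and a generalized least squares analysis in PROC MIXED to deal with dropout. Complier average causal effect and bootstrap mediation models follow later. Semester appears in none of these as covariate, stratum or interaction. Baseline is the only adjustment that is named.

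**The concern.** The two cohorts reach their 12-week visits at different times of year, and the outcomes are diet quality, physical activity, sleep and quality of life. A difference between Fall and Spring in any of these is plausible, though the documents give no figure for it. Baseline adjustment removes the part of such a difference that is already present at enrollment. It does not remove a difference that emerges by week 12, and the t-tests remove none of it.

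What remains has two effects. It adds to residual variance, so standard errors are wider than they need be. And because balance within semester is not stated as a design feature, the arms may differ by chance in their Fall/Spring mix, which moves the estimate in the trial actually run. At stake is some precision on H1 to H4. The plan also contains no analysis that would show whether the arm difference looks similar in the two cohorts.

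**Working it through.** **Inputs from the documents.** Total 300; two cohorts of about 150 (Protocol, Overview). The stated figures agree: 2 × 150 = 300. The documents give no alpha, power, SD, target effect or correlation, so 300 cannot be reproduced as a powered sample size.

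**Assumptions.** Two-sided alpha 0.05; 1:1 allocation, 150 per arm; no dropout; within-semester SD of 1; 50/50 semester split; semester difference d at 12 weeks of 0.1 to 0.5 SD; baseline-to-outcome correlation r as stated at each step.

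**1. Residual variance and standard error (r = 0.5).** After baseline adjustment the within-semester residual variance is 1 − 0.5² = 0.75. If baseline captures none of the semester difference, omitting semester adds d²/4. The share of residual variance is (d²/4)/(0.75 + d²/4), and the SE ratio is √(1 + (d²/4)/0.75).

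| d | Share, none captured | SE increase | Share, equal shift in baseline and outcome |
|---|---|---|---|
| 0.1 | 0.3% | 0.2% | 0.1% |
| 0.2 | 1.3% | 0.7% | 0.3% |
| 0.3 | 2.9% | 1.5% | 0.7% |
| 0.5 | 7.7% | 4.1% | 2.0% |

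The last column replaces d by d(1 − r) = 0.5d, because a baseline slope of about 0.5 removes half of a shift common to both measurements.

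**2. Power by formula, no baseline adjustment.** An effect of (1.960 + 0.842) × √(2/150) = 0.323 SD has 80.0% power with semester in the model. Without it the variance rises by the factor 1 + d²/4:

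| d | Variance factor | Power | N to offset the loss |
|---|---|---|---|
| 0.1 | 1.0025 | 79.9% | 301 |
| 0.2 | 1.0100 | 79.6% | 303 |
| 0.3 | 1.0225 | 79.1% | 307 |
| 0.5 | 1.0625 | 77.6% | 319 |

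**3. Simulation.** 6,000 runs per scenario, r = 0.4, simple randomization, true effect 0.3 SD. Power of ANCOVA on baseline against ANCOVA on baseline plus semester:

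- baseline and outcome both shifted by 0.3 SD: 79.4% and 79.4%;
- outcome only shifted by 0.3 SD: 79.1% and 79.9%;
- outcome only shifted by 0.5 SD: 77.1% and 79.7%, a loss of 2.6 points.

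The result depends modestly on r. With r = 0.5, d = 0.5 and nothing captured by baseline, the 4.1% wider SE takes 80.0% power to Φ(2.802/1.041 − 1.960) = 76.8%, a loss of about 3 points.

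**4. Type I error, same simulation with no effect.** Without the semester term, the t-test and baseline ANCOVA rejected in 4.9% to 5.6% of runs under simple randomization. The Monte Carlo standard error is √(0.05 × 0.95/6000) = 0.28 points, so this is compatible with 5%. With allocation balanced within semester and a 0.5 SD outcome shift, baseline ANCOVA was slightly conservative: 4.5%, against 5.2% with the term.

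**5. Chance imbalance under simple randomization.** The arm difference in semester share has SD √(2 × 0.25/150) = 0.058. A 1.96-SD imbalance is 0.113, about 11 percentage points. It shifts the estimate by 0.113 × d: 0.011, 0.023, 0.034 and 0.057 SD for d = 0.1, 0.2, 0.3 and 0.5. The standard error of the arm difference is √(2/150) = 0.115 SD unadjusted and √(0.75 × 2/150) = 0.100 SD after baseline adjustment.

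**6. What a by-semester comparison can show.** With 75 per arm in each cohort, the difference between the two semester-specific effects has SE √(4/75) = 0.23 SD unadjusted and √(0.75 × 4/75) = 0.20 SD adjusted for baseline. The two effects would have to differ by 1.96 times that, about 0.39 to 0.45 SD, for a 95% interval to exclude zero.

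**The case against.** The strongest case against is that this is a refinement and not a defect. Assignment is individual and randomized, so omitting a pre-randomization variable leaves the comparison unbiased on average. Under simple randomization the ordinary standard error already allows for chance imbalance in semester, as for any unadjusted covariate. That stands, and steps 3 and 4 bear it out. The semester difference is also wholly assumed, and only the top of the range costs more than about a point of power. That stands too. The SAP presents the trial as a largely descriptive feasibility study, which lowers the stakes further.

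Two stronger readings are tempting and should not be drawn.

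- A reader might infer that the intervention app's build differed between Fall and Spring, because Step 1: Study Orientation tells participants that "they may receive app updates throughout the 12-week period". That sentence concerns updates within a participant's own follow-up and does not say that the cohorts received different builds. If a build change did alter the treatment effect, that would be an arm-by-semester interaction, which a semester main effect cannot adjust for.
- A reader might infer that the SAP rules out every covariate but baseline. Its wording explains why ANCOVA is preferred to change scores; it is not a closed list. The plan is silent on semester; it does not exclude it.

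The objection does not remove the case for the change. Semester is a planned feature of enrollment, is known before randomization for everyone, and may matter at week 12 in a way baseline misses. Settling the choice in advance also avoids deciding whether to adjust after results are seen.

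**Conclusion.** The point holds as a minor, nearly free improvement. Two cohorts are planned, no model names semester, and no stratification by semester is stated. The cost is in precision and in conditional chance imbalance, not in validity. A reader might take the omission to mean a biased effect estimate or too many false positives; neither follows from a randomized design, and the simulated type I error stayed near 5%.

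For assumed semester differences of 0.1 to 0.5 SD, the simulated power loss is roughly 0 to 2.6 points, and about 3 points by formula in the least favorable case examined (r = 0.5, d = 0.5, nothing captured by baseline). It is near zero if semester moves baseline and outcome alike. Standard errors widen by at most about 4%. All of this rests on the assumed alpha, 1:1 ratio, unit SD, correlation of 0.4 to 0.5 and full follow-up, none of which the documents give.

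**What to change.** In the SAP, pre-specify semester (Fall 2016/Spring 2017) as a fixed effect in the ANCOVA and PROC MIXED models for all four outcomes. As a main effect this costs one degree of freedom, and no new data are needed. In PROC MIXED, crossing the term with visit would let it pick up a shift that emerges only by week 12, at one further degree of freedom for each additional visit.

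State in the Protocol whether randomization is stratified or blocked by semester.

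Report the arm difference for each outcome by semester, with confidence intervals, labeled as descriptive and with a note that about 75 per arm per cohort can reveal only large differences.

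These changes leave the t-tests and Hotelling's T2 as they are. The SAP does not say which analysis decides H1, so the gain reaches the primary conclusion only if that conclusion rests on the ANCOVA or the mixed model.

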## Recruitment

RCT participants will be recruited from the student population at LSU. Recruitment methods will include but are not limited to: flyers posted on campus and at businesses in the immediate area; social media posts; email and newsletter announcements by various departments and student organizations; online announcements through myLSU and SONA; recruitment tables set up at various campus events before and during the semester; recruitment presentations during classes and events; and by classified ads posted on Craigslist and the LSU newspaper, *The Reveille*.

Potential participants will be directed to an online baseline screening questionnaire to determine eligibility. They will also schedule their enrollment visit through this site.

## Preliminary Enrollment

A standardized enrollment procedure will be utilized for the RCT (**Appendix A**). From the recruitment materials, students will be directed to the **baseline screener questionnaire (Appendix B)** that is to be created by KB production staff. Students attempting to enroll in the study through PBRC will be directed to the enrollment website by sending a website link to the students' email.

Eligibility to participate in the RCT will be determined through the information provided by the student in the enrollment website. Students that are considered "screen fails" will be thanked and encouraged to participate in other research activities.

Students that meet eligibility criteria will be directed to the **online consent form (Appendix C)**. Here, students will be asked to read the consent information and indicate that they understand and agree to the terms of the study. Students unwilling to provide consent will be thanked for their interest and encouraged to participate in future research projects.

**Note:** This is considered an informal consent; a formal consent will be provided at the baseline enrollment meeting. The purpose of this informal consenting is to ensure that students are aware of the parameters of their participation prior to the baseline enrollment meeting to prevent attrition.

Students meeting eligibility requirements and providing online consent will be prompted to schedule a time for the baseline enrollment session (**Appendix D**). They will be provided a list of times that PBRC will be holding mass enrollments, and will indicate which of those sessions they are available to attend. Participants will also be prompted to schedule their 12-week follow-up visit at this time.

If a student is unavailable to attend one of these mass enrollment/follow-up sessions, they will be contacted by PBRC to arrange a one-on-one enrollment meeting.

**Note:** These one-on-one enrollment sessions are tentative and dependent on how quickly participants are being recruited. If recruitment fills quickly, only those with mass enrollment availability will participate in the study.

Participants will be assigned C-Numbers once they have registered for an enrollment meeting. The C-Numbers for RCT participants are assigned numerically beginning with C00-03-0201 and going up to C00-03-1000.

Upon completing the online enrollment process, participants will automatically receive an email confirmation for their enrollment and exit interview dates. Participants will receive an email reminder three days and one day prior to these meetings (**Appendix E**).

As a backup to the scheduler programming, KB and PBRC will also receive these email confirmations and reminders through their project-specific email accounts: [[contact]](mailto:[contact]) and [[contact]](mailto:[contact]).

## **Baseline Enrollment Meeting**

Based on their provided availability, participants will attend a baseline enrollment meeting on LSU campus. The following protocol will be employed at the baseline enrollment meetings:

1. Study Orientation: PBRC staff will provide an overview of the study and allow an opportunity for participants to ask questions
2. Written Consent, Identity Confirmation & W-9: Participants will be asked to provide written consent indicating they understand the terms of the study. Participants will confirm their identity during this step by showing PBRC staff their LSU ID, and they will be asked to complete a W-9 form.

3. Online Surveys: Participants will complete four **online surveys (Appendix G)** using a study tablet
4. Randomization: Participants will be randomized to a study condition
5. App Download: Participants will download their respective app
6. App Registration & Tutorial: Participants will be given a tutorial on how to use their study app and will be assisted in inputting personal information (class schedule, activity level, etc.) into the app
7. Exit Interview Scheduling: Participants will schedule a 12-week follow-up meeting with researchers

### **Step 1: Study Orientation**

PBRC staff will provide an overview of the study with a PowerPoint presentation. They will explain the purpose of the study, participant inclusion, study procedures, and participant compensation. Participants will be informed that they are expected to frequently use the app, and that their back end data will be tracked. Staff will notify participants that they will receive the 6-week interim survey link via email, and that they may receive app updates throughout the 12-week period. Participants will be instructed to download any app updates they may receive.

### **Step 2: Written Consent & Identity Confirmation**

Following the study orientation, participants will be asked to review and sign the consent forms (**Appendix F**). PBRC staff should bring extra copies in case participants want to keep a copy of the form. When collecting the signed consent forms, PBRC staff should confirm the participants' identities and LSU enrollment status by checking their student IDs. Only students whose identities and LSU statuses have been confirmed will be enrolled in the study.

Participants will be required to complete a W-9 form in order for LSU to process their compensation. Participants must provide their Social Security Numbers (SSNs) on this form.

### **Step 3: Online Surveys**

PBRC staff will hand out tablets for participants to complete the baseline surveys. Participants will first complete the KB-programmed baseline survey using the following link:

<https://www.questionpro.com/a/TakeSurvey?id=4781126>

After participants have finished the KB-programmed baseline survey, they will be instructed to take the ASA24 using the following link: <https://asa24.nci.nih.gov/>

PBRC staff will be required to enter the ASA24 username and password that is associated with the participant's Subject ID and C-Number. The list of ASA24 usernames and passwords is included in **Appendix H**. See below for information on C-Numbers.

## Tablets

The links for the online baseline survey, the ASA24, and the YouTube tutorial have been bookmarked on all six tablets provided to PBRC by KB. A majority of these tablets are password protected, and PBRC staff should be given the passwords to all of the tablets they will be using.

For the Apple products (iPads), PBRC staff may be required to know the KB email account associated with the tablets. The login information provided below is universal for all KB Apple products.

- Email address: [☰](#)
- Passcode: =

## Participant C-Numbers

PBRC staff can access participant C-Numbers through the Admin Healthy Detours Study site.

1. Visit [www.healthydetoursstudy.com](http://www.healthydetoursstudy.com) and click on the Admin link:
2. Click on an individual within the schedule to view his/her C-Number

## Step 4: Randomization

Participants should be instructed to notify PBRC staff once they have finished the ASA24. At this point, participants will be randomized to their study condition. The randomization link for each participant will be within the individual's Healthy Detours Schedule Page. PBRC staff will click on this link to determine the participant's study condition.

## Step 5: App Download

Based on the randomization assignment, participants will download either the Healthy Detours app or Calorie Counter by FatSecret. There are four scenarios associated with this step, dependent on randomization assignment and participant phone type.

### Control Group – Android User

1. From the Google Play store, search FatSecret, locate the Calorie Counter by FatSecret app, and install the app onto the participant's phone.

### Control Group – iPhone User

1. Locate the App Store on the participant's phone by searching for it in the drag down bar
2. Open the App Store and select "Search" in the bottom right corner
3. Search for FatSecret, locate the app, and download it onto the participant's phone

### **Intervention Group – Android User**

1. Go to the phone's settings.
2. Go to Security (you may have to select "More" to get to Security)

3. Find Unknown Sources and make sure it is checked
4. Open the internet browser in the phone and type in:  
<http://mdata.kleinbuendel.com/HeathyDetours/app/hdcurrent.apk>

5. The app will start to download. You will see a blinking arrow on the top left of the screen. When the arrow stops blinking, pull downward on the screen from the arrow. You will see the file name `hdcurrent.apk`. Select this file to open.
  
6. This pop-up page will appear, notifying users of the privacy agreement. Users must agree to this and Install.

7. Once installed, you may open the app.

### **Intervention Group – iPhone User**

1. Since KB programmers will know the randomization prior to the enrollment meeting, intervention group iPhone users will receive an email invite once they arrive to the meeting to beta test the Healthy Detours app. This will be sent to the email address linked to the participants' iTunes account. Participants should be instructed to not look at their phones while they are providing consent and completing the online surveys. When ready to install the app, open the TestFlight email and select "Start Testing"

2. You will be taken to this page and provided with a redemption code. This code should be written down for possible future use. If TestFlight has not already been installed, click on the blue link to download the program to the phone.
  
3. You will be taken to the Apple Store. Select "Get" and then "Install." Once the app has been installed, select "Open."

Accept TestFlight's Terms of Service and Apple's Privacy Policy and indicate that TestFlight can send the user notifications

4. Healthy Detours should automatically appear in the user's queue. Select "Install," and then "Open." Once the app is open, allow Healthy Detours to access the participant's location. After selecting "Allow", you will be brought to the Registration Page.

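### Intervention-arm iPhone users are emailed the Healthy Detours invite on arrival, before written consent and the baseline diet recall, so part of one arm can learn its assignment early

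*Protocol*

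**What the plan says.** The protocol's section *Baseline Enrollment Meeting* lists the steps as orientation, written consent with identity check, online surveys, randomization, then app download. The detailed sections keep that order.

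- *Step 2*: "Following the study orientation, participants will be asked to review and sign the consent forms".
- *Step 3*: "After participants have finished the KB-programmed baseline survey, they will be instructed to take the ASA24 using the following link".
- *Step 4*, once the ASA24 is finished: "At this point, participants will be randomized to their study condition". Staff do this by clicking a link on the participant's schedule page.

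The online agreement obtained before the meeting does not replace written consent. *Preliminary Enrollment* states: "This is considered an informal consent; a formal consent will be provided at the baseline enrollment meeting".

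Under Step 5, *Intervention Group – iPhone User* gives a different timing: "Since KB programmers will know the randomization prior to the enrollment meeting, intervention group iPhone users will receive an email invite once they arrive". The invite is for the Healthy Detours app and goes to the address linked to the participant's iTunes account. The same paragraph carries the only safeguard: "Participants should be instructed to not look at their phones while they are providing consent and completing the online surveys".

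The download instructions for control participants and for intervention-arm Android users describe no early message.

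In the SAP, the primary hypothesis (H1) uses the HEI calculated from the ASA24. The analysis paragraph plans simple t-tests followed by "analysis of covariance to assess the outcome results adjusted for baseline (rather than change from baseline").

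**The concern.** Assignment should stay hidden from a participant until consent is signed and baseline data are complete. Here the protocol itself sends an arm-specific message before either has happened, to one arm and one phone type.

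Two things could then depend on arm:

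- **Who signs.** A student who infers the arm can use that in deciding whether to consent. Losses of this kind occur before enrollment, so they would affect every analysis and would not show up in the SAP's planned examination of dropouts.
- **What is reported at baseline.** The ASA24 is self-reported, and the baseline HEI is the covariate for the primary outcome. If intervention students who know their arm report a better baseline diet, the covariate adjustment works against Healthy Detours. If they report a worse one, it works in its favor.

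Participants will know which app they use by week 12 in any case. What early disclosure adds is its effect on consent and baseline.

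**Working it through.** **Order of events.** Placing the email in the meeting sequence gives:

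| Order | Event | Protocol section | Phone instruction applies? |
|---|---|---|---|
| 1 | Arrival; invite sent to intervention iPhone users | Intervention Group – iPhone User | Not named |
| 2 | Orientation | Step 1 | Not named |
| 3 | Written consent | Step 2 | Yes |
| 4 | Baseline survey, then ASA24 | Step 3 | Yes |
| 5 | Staff click the link; arm revealed | Step 4 | – |
| 6 | App download | Step 5 | – |

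The invite precedes all of rows 2 to 5. A student who looks at the phone in rows 1 or 2 breaks no instruction. This part needs no assumptions.

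**Size.** The plan gives no figure to reproduce: 300 students are stated, but no allocation ratio, alpha, power, SD or iPhone share. What follows is illustrative.

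Assumptions:

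- 150 per arm (300 / 2)
- iPhone share p = 0.4 to 0.8
- proportion of those invited who look early and infer the arm, r = 0.1 to 0.5
- shift in their reported baseline HEI, d = 0.3 SD in either direction
- ANCOVA slope of the 12-week value on baseline, b = 0.4
- no controls affected

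*Students exposed.* Invited before consent: 150 × 0.4 = 60 to 150 × 0.8 = 120, against 0 controls. Looking early: 60 × 0.1 = 6 to 120 × 0.5 = 60.

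*Baseline imbalance* = p × r × d, and *ANCOVA bias* = −b × imbalance (sizes shown):

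| Case | p | r | Imbalance (SD) | ANCOVA bias (SD) |
|---|---|---|---|---|
| Low | 0.4 | 0.1 | 0.012 | 0.005 |
| Mid-range | 0.6 | 0.3 | 0.054 | 0.022 |
| Mid share, highest looking rate | 0.6 | 0.5 | 0.090 | 0.036 |
| High | 0.8 | 0.5 | 0.120 | 0.048 |

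*Benchmark.* With two-sided 5% and 80% power (both assumed), the detectable difference is 2.80 × √(2/150) = 0.323 SD for a t-test. For ANCOVA it is 0.323 × √(1 − 0.4²) = 0.296 SD. The mid-range bias is 0.022 / 0.296 = 7% of that; at the highest looking rate it is 0.036 / 0.296 = 12%.

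*Wider inputs.* Let s be the share of the whole intervention arm that reads the email. With b = 0.3 to 0.6, s = 0.05 to 0.5 and d = 0.1 to 0.3 SD, the bias runs from 0.3 × 0.05 × 0.1 = 0.0015 SD to 0.6 × 0.5 × 0.3 = 0.09 SD.

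*Other analyses.* A t-test on the 12-week value alone is not affected by baseline reporting. A t-test on change would carry the imbalance in full (0.012 to 0.12 SD above). The SAP does not say which its simple t-tests are. The same holds for the Hotelling's T² analysis on pre and post measures, if it uses change scores.

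Selective consent is not sized, because nothing in the documents bears on its rate.

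**The case against.** The protocol anticipated the problem. Students are told not to look at their phones during consent and surveys, the two steps at issue, and the surveys are done on study tablets. That narrows the gap without closing it: the instruction is only verbal, the email is already on the phone, and arrival and orientation are left open.

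The email may not reveal the arm. That depends on what students have been told about the two apps, which is in consent forms and orientation slides not available here. The study website itself carries the Healthy Detours name, so the invite could pass for routine study mail. This stands as a limit: the finding is that students can learn their arm, not that any did.

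Selective refusal would require opening the email, inferring the arm and then declining, after agreeing online and with $200 offered for completing the posttest. It is possible, but nothing shows it is likely.

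An assignment generated in advance and revealed at the click is compatible with Step 4, and early knowledge is documented only for KB programmers, not for the PBRC staff who enroll. Both points are fair. The defect is the timing of the email, not the existence of an advance list.

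The bias figures rest wholly on assumptions, and the SAP calls the trial a largely descriptive feasibility study. That argues against a severe rating, not against a cheap correction. One simplification may also be wrong: at mass sessions, controls who see others receive invites might infer their own arm, so exposure need not be confined to one arm.

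**Conclusion.** The concern holds. Followed as written, the protocol sends an arm-specific message before orientation, written consent, the baseline survey and the ASA24, and its one safeguard does not name the first part of that window. Confidence is high for the sequence and low for the size. Under the assumptions above, the ANCOVA bias is small and could go in either direction; the risk to consent cannot be quantified. The case for change rests on an avoidable gap in concealment at consent and baseline, not on a large calculated bias. It should be fixed, but it does not by itself undermine the trial.

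**What to change.** Reconcile *Step 4: Randomization* with *Intervention Group – iPhone User*. Send the TestFlight invite, manually or automatically, only after written consent, the baseline survey and the ASA24 are recorded as complete and staff have clicked the randomization link. Until that is in place, extend the instruction about phones to cover arrival and orientation.

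The cost is a change of protocol wording and, if invites are sent by hand, a message from session staff to KB at the click. Intervention iPhone users would wait briefly for the email. No change to the study website is required.

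Preferably, the assignment would also be generated, or released to KB, only at the click. This is optional. It may need a website change whose extent the documents do not show, and the main fix does not depend on it.
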